9.5.1.5 Safety Assessments

Safety assessments will consist of monitoring and recording all AEs, including all Common Terminology Criteria for Adverse Events (CTCAE) v4.0 grades (for both increasing and decreasing severity), and SAEs including platelet transfusion-related complications; regular monitoring of hematology, blood chemistry, and urine values; periodic measurement of vital signs and electrocardiograms (ECG); the performance of physical examinations; and Doppler sonography as detailed in [Table 5](#).

An independent DSMB will be established in order to ensure the safety of the subjects.

ADVERSE EVENTS AND OTHER EVENTS OF INTEREST

An AE is any untoward medical occurrence in a subject or clinical investigation subject administered an investigational product. An AE does not necessarily have a causal relationship with the medicinal product. For this study, the study drug is avatrombopag

The criteria for identifying AEs are:

- Any unfavorable and unintended sign (including an abnormal laboratory finding), symptom, or disease temporally associated with the use of an investigational product, whether or not considered related to the investigational product

- Any new disease or exacerbation of an existing disease
- Any deterioration in nonprotocol-required measurements of a laboratory value or other clinical test (eg, ECG or x-ray) that results in symptoms, a change in treatment, or discontinuation of study drug
- Recurrence of an intermittent medical condition (eg, headache) not present at pretreatment (Baseline)
- An abnormal laboratory test result should be considered an AE if the identified laboratory abnormality leads to any type of intervention, whether prescribed in the protocol or not.

A laboratory result should be considered by the investigator to be an AE if it:

- Results in the withdrawal of study drug
- Results in withholding of study drug pending some investigational outcome
- Results in an intervention, based on medical evaluation (eg, potassium supplement for hypokalemia)
- Results in any out of range laboratory value that in the investigator's judgment fulfills the definitions of an AE with regard to the subject's medical profile

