- Increases in severity compared with baseline by ≥ 2 CTCAE grades (see [Appendix 1](#) for CTCAE v 4.0), with the exception of lymphocytes, albumin, cholesterol, glucose, and phosphate. For these tests, any change of ≥ 2 grades will be evaluated by the investigator to determine if it is of clinical significance and, if so, will be considered an AE.

All AEs observed during the study will be reported on the CRF. All AEs, regardless of relationship to study drug or procedure, should be collected beginning from the time the subject signs the study ICF through the last visit. Serious AEs will be collected for 30 days after the last dose.

Abnormal laboratory values should not be listed as separate AEs if they are considered to be part of the clinical syndrome that is being reported as an AE. Any laboratory abnormality considered to constitute an AE should be reported on the Adverse Event CRF.

It is the responsibility of the investigator to review all laboratory findings in all subjects and determine if they constitute an AE. Medical and scientific judgment should be exercised in deciding whether an isolated laboratory abnormality should be classified as an AE.

Abnormal ECG (QTc, corrected for heart rate) results, if not otherwise considered part of a clinical symptom that is being reported as an AE, should be considered an AE if the QTc interval is >450 ms and there is an increase of >60 ms from baseline. Any ECG abnormality that the investigator considers as an AE should be reported as such.

All AEs must be followed for 30 days after the subject's last dose, or until resolution, whichever comes first.

Every effort must be made by the investigator to categorize each AE according to its severity and its relationship to the study treatment.

ASSESSING SEVERITY OF ADVERSE EVENTS

Adverse events will be graded on a 5-point scale according to CTCAE v4.0¹⁸ as follows:

- Grade 1 = Mild: asymptomatic or mild symptoms; clinical or diagnostic observations only; intervention not indicated
- Grade 2 = Moderate: minimal, local, or noninvasive intervention indicated; limiting age-appropriate instrumental activities of daily living
- Grade 3 = Severe or medically significant but not immediately life threatening hospitalization or prolongation of hospitalization indicated; disabling; limiting self-care activities of daily living
- Grade 4 = Life-threatening consequences: urgent intervention indicated
- Grade 5 = Death related to AE

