Investigators will report CTCAE grades for all AEs (for both increasing and decreasing severity). All AEs reported using CTCAE classification and graded as 4 or 5 are to be considered serious. The criteria for assessing severity are different from those used for seriousness (see Serious Adverse Events and Other Events of Interest for the definition of an SAE).

ASSESSING RELATIONSHIP TO STUDY TREATMENT

Items to be considered when assessing the relationship of an AE to the study treatment are:

- Temporal relationship of the onset of the event to the initiation of the study treatment
- The course of the event, especially the effect of discontinuation of study treatment or reintroduction of study treatment, as applicable
- Whether the event is known to be associated with the study treatment or with other similar treatments
- The presence of risk factors in the study subject known to increase the occurrence of the event
- The presence of nonstudy, treatment-related factors that are known to be associated with the occurrence of the event

CLASSIFICATION OF CAUSALITY

Not Related A causal relationship between the study treatment and the AE is not a reasonable possibility.

Related A causal relationship between the study treatment and the AE is a reasonable possibility. The investigator must further qualify the degree of certainty as “possible” or “probable.”

SERIOUS ADVERSE EVENTS AND OTHER EVENTS OF INTEREST

A SAE is any untoward medical occurrence that at any dose:

- Results in death
- Is life-threatening (ie, the subject was at immediate risk of death from the adverse event as it occurred; this does not include an event that, had it occurred in a more severe form or was allowed to continue, might have caused death)
- Requires inpatient hospitalization or prolongation of existing hospitalization
- Results in persistent or significant disability/incapacity
- Is a congenital anomaly/birth defect (in the child of a subject who was exposed to the study drug)

Other important medical events that may not be immediately life-threatening or result in death or hospitalization but, when based on appropriate medical judgment, may jeopardize the subject or may require intervention to prevent 1 of the outcomes in the definition of SAE listed above should also be considered SAEs. Medical and scientific judgment should be exercised in deciding whether expedited reporting is appropriate in such situations.

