- Is outside normal limits at baseline and increases in severity to the sponsor's grading criteria for laboratory values of Grade 4 or above. These abnormalities are automatically considered to be serious, with the exception of expected and reproducible hematologic abnormalities.
- Is otherwise considered by the investigator to meet serious criteria as defined in [Section 9.5.1.5](#) (Serious Adverse Events and Other Events of Interest)

Significant laboratory abnormalities should not be listed as separate AEs or SAEs if they are considered to be part of the clinical syndrome that is being reported as an AE or SAE.

REPORTING OF STUDY-SPECIFIC EVENTS

Study-specific events (ie, recurrence of thrombocytopenia [defined as a platelet count of $<10 \times 10^9/L$ and $10 \times 10^9/L$ less than baseline count within 30 days of discontinuation]); thromboembolic events; bleeding events (WHO Grade 2 to 4); and platelet transfusion-related complications should be entered on the Adverse Event CRF and reported using the procedures detailed in Reporting of Serious Adverse Events ([Section 9.5.4.1](#)), even if the study-specific event does not meet serious criteria. If the event does not meet serious criteria, it must still be reported using the SAE form and in an expedited manner but should be noted as nonserious on the SAE form and the Adverse Event CRF. All liver transplantations will be captured as SAEs.

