#### 4 DETERMINATION OF SAMPLE SIZE

The proposed sample size was based on comparisons of the primary efficacy variable, with the response rate defined as the proportion of subjects who do not require a platelet transfusion or any rescue procedure for bleeding after randomization and up to 7 days following an elective procedure. Based on clinical opinion and the published results of a similar compound in adults with thrombocytopenia associated with liver disease (ELtrombopag EVALuated for its Ability to overcome Thrombocytopenia and Enable procedures [ELEVATE] study [Afdahl, 2012]), the response rate in the placebo group is assumed to be 18%. Within each baseline platelet count cohort, a sample size of 100 randomized subjects, 67 subjects for avatrombopag and 33 subjects for placebo, would have greater than 90% power to detect an absolute difference of 35% between the avatrombopag response rate and the placebo response rate assuming 18% response rate for placebo using Fisher's Exact tests with a 2-sided  $\alpha=0.05$ . The hypothesized treatment group difference was based on platelet count changes found in the Phase 2 study (E5501-G000-202) and dose-response modeling using data from that study and others in the project development. Based on the baseline data in the Phase 2 study and assuming these were projected to be similar for this study, it was anticipated that this study would enroll roughly half of the total number of subjects in each of the 2 baseline platelet count cohorts to make the total sample size of 200 randomized subjects, 133 subjects for avatrombopag and 67 subjects for placebo.

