### **5.6.2 Adverse Events**

The AE verbatim descriptions (investigator terms from the CRF) will be classified into standardized medical terminology using the Medical Dictionary for Regulatory Activities (MedDRA). Adverse events will be coded to the MedDRA (Version 15.1 or higher) lower level term (LLT) closest to the verbatim term. The linked MedDRA preferred term (PT) and primary system organ class (SOC) will also be captured in the database.

A treatment-emergent AE (TEAE) is defined as an AE that

- Emerged during treatment (up to 30 days after the last dose of study drug), having been absent at pretreatment (Baseline) or
- Reemerged during treatment (up to 30 days after the last dose of study drug), having been present at pretreatment (Baseline) but stopped before the last dose of study drug plus 30 days, or
- Worsened in severity during treatment (up to 30 days after the last dose of study drug) relative to the pretreatment state, when the AE was continuous.

Only those AEs that are treatment emergent will be included in summary tables. All AEs, treatment emergent or otherwise, will be presented in subject data listings.

An overview table of TEAE, including number of subjects with TEAEs, treatment-emergent serious adverse events (SAEs), deaths, severe TEAEs, study drug related TEAEs, TEAEs leading to study drug withdrawal will be provided. In addition, the following summaries will be produced:

- Incidence of TEAEs by SOC and PT
- Incidence of treatment-related TEAEs by SOC and PT
- Incidence of procedure-related TEAEs by SOC and PT
- Incidence of TEAEs after procedure (with an onset date on or after Procedure Day) by SOC and PT
- Incidence of TEAEs related to platelet transfusion complications by SOC and PT
- Incidence of TEAEs by SOC, PT, and common terminology criteria for adverse events (CTCAE) grade
- Incidence of treatment-related TEAEs by SOC, PT, and CTCAE grade
- Incidence of TEAEs by SOC, PT, and relationship to treatment

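### A low Procedure Day platelet count that leads to the anticipated transfusion can be reported as an AE, and as serious below 25 × 10^9/L; the reporting rules conflict, and any such events fall mainly on placebo

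*Protocol*

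**What the plan says.** Provisions that bring a low count into AE reporting:

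- Protocol 9.5.1.5: an abnormal laboratory result "should be considered an AE if the identified laboratory abnormality leads to any type of intervention, whether prescribed in the protocol or not". A second trigger in the same section covers results that lead to an intervention after medical evaluation.
- The only tests named as exceptions in that section ("with the exception of lymphocytes, albumin, cholesterol, glucose, and phosphate") are exempt from the two-grade-increase rule alone. Platelets are not among them.
- Protocol Appendix 1 and SAP 13.1 grade platelets below 25 × 10^9/L as Grade 4, and 25 to below 50 as Grade 3.
- Protocol 9.5.1.5 on severity: "All AEs reported using CTCAE classification and graded as 4 or 5 are to be considered serious".

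Provisions that pull the other way:

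- Protocol 9.4.7: when therapy is given for a condition present at study entry, that condition is recorded as medical history.
- Protocol 9.5.1.5: "Medical and scientific judgment should be exercised in deciding whether an isolated laboratory abnormality should be classified as an AE".
- Protocol 9.5.4.3: a result that is abnormal at baseline and rises to Grade 4 is automatically serious, "with the exception of expected and reproducible hematologic abnormalities".
- SAP 5.6.2, matching Protocol 9.7.1.8: "Only those AEs that are treatment emergent will be included in summary tables". Treatment emergent means new, re-emerging or worsened in severity.

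Protocol 9.7.1.8 and SAP 5.6.3 leave platelet count out of the descriptive laboratory summaries because it is an efficacy parameter. No matching rule exists for AEs.

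**The concern.** Inclusion criterion 3 admits only subjects expected to need a platelet transfusion unless their count rises. The event that makes a subject a primary-endpoint failure, a low count followed by transfusion, therefore also meets the literal laboratory-AE rule. Transfusion is expected more often on placebo, so recording it again as an AE or SAE raises placebo totals more than avatrombopag totals. Avatrombopag then looks safer for a reason that belongs to efficacy.

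The conflicting provisions also leave each of about 80 to 100 sites to choose its own reading. Evaluating safety is a secondary objective and rests on descriptive tables, so an arm-dependent reporting artefact in the overall TEAE and SAE rows matters.

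**Working it through.** **1. The plan's own figure.** With 67 avatrombopag and 33 placebo subjects per cohort, 53% versus 18% response, and Fisher's exact test at two-sided 0.05, exact enumeration gives power 0.926. This agrees with the stated figure of more than 90%.

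**2. Ceiling for the single term.** Planned non-response is 1 − 0.18 = 82% on placebo and 1 − 0.53 = 47% on avatrombopag. That is 67 × 0.82 ≈ 55 of 67 placebo and 133 × 0.47 ≈ 63 of 133 avatrombopag subjects, 35 points apart. Non-response also includes rescue without transfusion and missing outcomes counted as transfused, so this bound cannot be reached.

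**3. What passes the filter if judged by grade.** Every eligible subject has a mean baseline count below 50, which is already Grade 3 or 4. Severity is CTCAE grade (Protocol 9.5.1.5), so a fall from 35 to 33 is not worsening. A subject already below 25 cannot worsen in grade. The main route into the tables is Grade 3 falling to Grade 4.

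The documents give no platelet variability, so I simulated a no-drug population.

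- Assumptions: true-count mean 40 to 50, between-subject SD 10 to 15, within-subject SD 5 to 11.
- Entry rule applied: two counts, neither above 60, mean below 50. A third count then stands for Procedure Day.
- Low cohort, baseline 25 or more and Procedure Day below 25: 4.5% to 16.0%, or 33 × 0.045 = 1.5 to 33 × 0.160 = 5.3 placebo subjects.
- High cohort: 0.1% to 8.0%, at most 33 × 0.080 = 2.6 placebo subjects.
- Using the last predose count as baseline instead of the mean gives 4.4% to 15.9% in the low cohort.

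These shares come before requiring a transfusion or a report. Even if no avatrombopag subject fell a grade, they would cap the between-arm gap for the term at about 4 to 16 points in the low cohort and 0 to 8 in the high cohort.

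**4. What passes if treatment emergence is taken from onset date alone.** Let b be the AE rate from other causes, f the share of non-responders tabulated, and q planned non-response. The AE rate is b + (1 − b) × f × q, so the gap (avatrombopag minus placebo) is −(1 − b) × f × 0.35. Both b and f are assumptions.

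- f = 1: b = 30% gives −0.70 × 0.35 = −24.5 points; b = 60% gives −0.40 × 0.35 = −14 points.
- f = 0.25: −6.1 and −3.5 points.
- SAEs, with 10% to 40% of non-responders transfused below 25 and counted as serious, and an other-cause SAE rate of 3% to 10%: about −3 to −14 points.
- f = 0: no artefact.

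**5. Seriousness.** A subject who falls from Grade 3 to Grade 4 is covered by two rules. The severity text in Protocol 9.5.1.5 makes the AE serious without exception. Protocol 9.5.4.3 requires the abnormality on the AE form but exempts it from automatic seriousness if it is expected and reproducible. Nothing says which rule governs.

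**The case against.** The strongest reply is that the plan already contains the answer. Thrombocytopenia is the entry condition, so Protocol 9.4.7 routes a stable low count with its anticipated transfusion to medical history. Investigator judgment applies to isolated laboratory results. An unworsened count goes to listings only. Safety is not hypothesis-tested, and a platelet term would show as its own preferred-term row. The CRF Completion Guidelines and the derivation specifications, which are not in these documents, may settle the matter.

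Much of this stands. It rules out the reading that every transfused low count becomes a tabulated AE, and that every one below 25 becomes an SAE. It does not remove the conflict. Protocol 9.4.7 concerns where a condition is recorded, while the laboratory rule covers any intervention, prescribed or not, and neither refers to the other. Judgment without a stated rule invites uneven coding. A separate row makes the term visible but does not take it out of the overall TEAE and SAE totals. Neither document says whether baseline thrombocytopenia is compared by grade when treatment emergence is derived.

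**Conclusion.** The concern holds in a limited form. The provisions contradict each other on whether a low count leading only to the anticipated transfusion is an AE, and on whether it is serious below 25. The direction is clear: any such events raise placebo totals more.

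A reader might infer a 35-point bias in the safety tables. The documents do not support that: it is an unreachable ceiling for one term and ignores the treatment-emergent filter. If worsening is judged by grade, the events that reach the tables are mainly Grade 3 to Grade 4 falls, roughly 4 to 16% of low-cohort and 0 to 8% of high-cohort counts without drug. These figures rest on assumed variability and come before requiring a transfusion. The wider figures (14 to 25 points on overall AE rates if all are tabulated, 3.5 to 6 if a quarter are) apply only if treatment emergence is derived from onset date alone and under the assumed other-cause rates.

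**What to change.** - **Reporting.** Reconcile Protocol 9.4.7, the laboratory-AE and Grade 4 provisions of 9.5.1.5, and 9.5.4.3. They should say whether, and how seriously, a count no worse in grade than baseline that leads only to the anticipated pre-procedure transfusion is reported. Genuine worsening must stay reportable. A blanket exemption would lose, for example, a fall from 45 to 12 without bleeding, which does not meet the recurrence-of-thrombocytopenia definition (below 10).
- **SAP 5.6.2.** State that treatment emergence of platelet-count terms is judged against the baseline grade, and which baseline is meant: the mean of the two entry counts, or the last predose value that SAP 5.6 uses by default.
- **Tables.** Repeat the overall TEAE and SAE summaries without low-platelet-count terms reported only because of pre-procedure transfusion. Fix the selection rule before unblinding, and say how it treats falls to Grade 4, which Protocol 9.5.4.3 puts on the AE form in their own right.

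The cost is one reporting clarification, one SAP sentence and one or two extra tables. The repeated tables also cover data already collected.

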9.5.1.6 Other Assessments

HEALTH ECONOMIC ASSESSMENTS

Health economic parameters will be collected at each visit (as appropriate). Health care resource utilization, including any rescue treatment, procedure, and laboratory test for bleeding including the number of transfused platelet units, the supply from which the transfused platelet units were procured including whole blood platelets from a random donor pool (if known) with or without leukocyte depletion, as an apheresis product (as platelets alone) from a single donor and/or autologous blood donation, number of hospital days, number of intensive care bed-days, number of outpatient visits to the hospital's outpatient department, the clinic, the physician's office, home health care or other place of service, and health care resource utilization related to other transfusion-related complications during all scheduled and unscheduled visits will be collected in the CRF.

9.5.2 Schedule of Procedures/Assessments

9.5.2.1 Schedule of Procedures/Assessments

[Table 5](#) presents the schedule of procedures/assessments for the study.

Table 5 Schedule of Procedures/Assessments in Study E5501-G000-311

Phase Period Visit	Prerandomization	Randomization			Follow-Up	
	Screening	Baseline	Treatment	Procedure Day	5	6 ^c
Day	1	2	3	4 ^{a, b}	5	6 ^c
Day	Days -14 to -1	Day 1	Day 4 (±1 day)	Day 10 (+3 days)	7 Days Postprocedure (+3 days)	Day 35 (+3 days)
Procedures/Assessments						
Subject informed consent	X					
Inclusion/Exclusion criteria	X	X				
Demographics	X					
Medical history	X					
CTP and MELD Scores	X					
BCLC grade ^d	X					
Prior/concomitant medications	X	X	X	X	X	X
Health care resource use		X	X	X	X	X
Adverse events	X	X	X	X	X	X
Physical examination ^e	X			X	X	X
Vital signs (including height, weight)	X ^f	X		X	X	X
ECG (12-lead)	X	X	X			X
Hematology (including platelet count by local laboratory) ^g	X ^h	X ^h	X	X	X	X
Coagulation	X			X		X
Serum chemistry, liver function tests, CPK with fractionation, urinalysis ⁱ	X			X		X

Table 5 Schedule of Procedures/Assessments in Study E5501-G000-311

continued						
Phase	Prerandomization	Randomization			Follow-Up	
Period	Screening	Baseline	Treatment	Procedure Day	Postprocedure	
Visit	1	2	3	4 ^{a,b,c}	5	6 ^d
Day	Days -14 to -1	Day 1	Day 4 (±1 day)	Day 10 (+3 days)	7 Days Postprocedure (+3 days)	Day 35 (+3 days)
HIV serology	X					
Pregnancy testing ^j	X	X		X		X
Doppler sonography	X ^k				X ^l	
Assessment of platelet transfusion ^m		X	X	X	X	
Assessment of any rescue procedure for bleeding ⁿ		X	X	X	X	
Serum TPO		X		X		X
Platelet function tests ^o		X	X	X		
Randomization		X				
PK blood sampling		X ^p	X ^{p,q}			
Study drug dosing ^{r,s}		X	X			
Dispense dosing diary ^t		X				
Retrieve/review dosing diary			X	X		
Collect study drug, if applicable				X		
Bleeding assessment (WHO and BARC)		X	X	X	X	X

BARC = Bleeding Academic Research Consortium; BCLC = Barcelona Clinic Liver Cancer; CPK = creatine phosphokinase; CTP = Child-Turcotte-Pugh; ECG = electrocardiogram; HIV = human immunodeficiency virus; MELD = Model For End-stage Liver Disease; PK =

Table 5 Schedule of Procedures/Assessments in Study E5501-G000-311

pharmacokinetics; TPO = thrombopoietin; WHO = World Health Organization

- a: Subjects will undergo their elective procedure within 5 to 8 days of their last dose of study drug (ie, Study Day 10 to 13), and after completing the Procedure Day assessments.
- b: Visit 4 (Procedure Day) assessments will also occur when any subject has been withdrawn or discontinued early from the study for any reason.
- c: Visit 6 (Day 35) assessments will also occur when any subject has been withdrawn or discontinued early from the study for any reason.
- d: BCLC grade is only for subjects with hepatocellular carcinoma.
- e: Comprehensive physical examination at Screening and targeted physical examination at all subsequent visits.
- f: Height will be recorded at Screening (Visit 1) only.
- g: Hematology must be taken prior to any platelet transfusion
- h: Independent platelet counts performed by a local laboratory at Screening and Baseline must be at least 1 day apart with neither platelet count $>60 \times 10^9/L$. The mean of these 2 platelet counts (mean baseline platelet count) must be $<50 \times 10^9/L$ (as per Inclusion Criterion #2), to be eligible to participate in the study.
- i: Complete urinalysis will be performed at Screening and dipstick analysis at all subsequent visits. If urine dipstick is abnormal, a complete urinalysis will be required. After the Screening measurement, fractionation will only be analyzed by the central laboratory in the event CPK level is abnormal.
- j: For females of childbearing potential or who have been amenorrheic for less than 12 months. Serum beta-human chorionic gonadotropin pregnancy testing will be performed at Screening (Visit 1). Urine pregnancy testing will be performed at Visits 2, 4, and 6.
- k: Portal vein flow velocity will be assessed at this visit. Subjects will be required to have a main portal vein blood flow velocity rate of ≥ 10 cm/second at Screening to be eligible for the study.
Three main portal vein blood flow velocity measurements, lasting no less than 4 seconds, will be recorded, and the mean of the 3 values recorded as the final reading.
The Doppler sonography and flow rate assessment can be completed at any time during the Screening Period with results available prior to randomization.
- l: Only subjects whose preprocedural platelet count exceeds $200 \times 10^9/L$ will be required to have a Doppler assessment at Visit 5. For any subjects where the presence of a portal vein thrombosis (PVT) is suspected, confirmation of diagnosis via computerized tomography scan or magnetic resonance imaging, should be performed and treatment for PVT initiated per local guidelines.
- m: Number of transfusions administered (if used), along with start and end dates/times, will be recorded.
- n: Any rescue procedure for bleeding, including number of transfusions administered (if used), along with start and end dates/times, will be

Table 5 Schedule of Procedures/Assessments in Study E5501-G000-311

- recorded.
- o: Platelet function tests will be performed at selected sites. Flow cytometry will be performed at Visits 2, 3, and 4. Platelet aggregometry will be performed on Day -14 to 1 (Visit 1 or 2) before dosing and on the Procedure Day (Day 10) (revised per Amendment 02).
 - p: On Visit 2 (Day 1), 1 PK sample will be collected between 2 to 6 hours after dosing.
 - q: On Visit 3 (Day 4 ±1), 2 PK samples will be collected: predose (within 2 hours prior to dosing) and between 2 to 6 hours after dosing.
 - r: Subjects will be randomized to receive placebo or avatrombopag as follows:
 - Group A (avatrombopag, lower baseline platelet count): 60 mg avatrombopag (3 × 20-mg tablets) once daily on Days 1 through 5
 - Group B (placebo, lower baseline platelet count): placebo (3 × 20-mg matching placebo tablets) once daily on Days 1 through 5
 - Group C (avatrombopag, higher baseline platelet count): 40 mg avatrombopag (2 × 20-mg tablets) once daily on Days 1 through 5
 - Group D (placebo, higher baseline platelet count): placebo (2 × 20-mg matching placebo tablets) once daily on Days 1 through 5
 - s: All doses of study drug will be taken with a meal.
 - t: Subjects will receive a dosing diary in which they are to record the dates and times of their study drug doses.

